**J. Community-Based Participatory Research (if applicable)**

1. Participants and the nature of their involvement:  
Drs [name] and [name] are ophthalmologists in the community who are also involved in the study. They will serve the roll to identify subjects in their office and refer them to the neurology clinic for evaluation and enrollment into the study.
2. Cultural issues: We do not anticipate any cultural issues.
3. Origin of the research question: N/A
4. Risks and Benefits: N/A
5. Study Description and Process: N/A
6. Return of results: N/A
7. Sustainability: N/A

**L. Assessment of Subject Safety and Development of a Data and Safety Monitoring Plan**

1. Elements of the plan include:
  - a. Persons/groups who will review the data (study team; independent safety monitor, data monitoring committee or formal DSMB) Study personnel
  - b. Data/events that will be reviewed - All collected data will be reviewed
  - c. Frequency of review - Once a month
  - d. Types of analyses to be performed
  - e. Safety-related triggers that would cause the PI to stop or alter the study  
We do not anticipate any safety related triggers that would cause the study to be stopped or altered
2. We do not anticipate any adverse events in the study. In case of any unanticipated problems we will have a safety monitor appointed for the study. Any adverse event from the drug will be treated in timely fashion. The subject will be withdrawn from the study in case of any adverse events.
3. The subject will be withdrawn from the study in case of any adverse events to ensure safety.

### **III. Subject Participation**

#### **A. Recruitment:**

1. Subjects in the age group of 18-65years will be recruited from the neurology clinics at the University of Kansas Medical Center located at Landon Center of Aging, [name]; Indian Creek Neurology Clinic located at [name] and the Spine Center Neurology Clinic located at [name].
2. Recruitment will be conducted by the study personnel (physicians)
3. N/A
4. N/A

**B. Screening Interview/questionnaire:** No specific screening interview or questionnaire will be performed. Subjects will be identified and enrolled during their neurology office visit.

#### **C. Informed consent process and timing of obtaining of consent**

- 1 Physicians (PI and Co-I)
- 2 A detailed verbal and written informed consent will be provided to the subjects. They will then be given some time to go over the details and make a thoughtful decision. All questions will be answered by the study personnel providing the consent.
- 3 The study personnel (physicians, PI and Co-I) will determine whether the subject (age 18-65years) is able to give an informed consent.

**D. Alternatives to Participation:** None

**E. Costs to Subjects:** Subjects will be identified and enrolled from their office visit. The subject's insurance company will pay for costs of clinical care just like any usual office visit. The only test which will be done as a part of the study, is the dipstick urine pregnancy screen the cost of which will be budgeted in the study budget.

**F. How new information will be conveyed to the study subject and how it will be documented:** Any new information made available will be conveyed to the subjects at either their in person visits or via phone calls.

**G. Payment, including a prorated plan for payment:** Subject honorarium/shipping: The end of study visit is not a clinic visit but a research visit. We will provide subjects \$25 to offset the cost of travel and food for this visit. For the interim visit, for the subject who can return to pick up their medication, we are offsetting the cost of travel and food for this visit by providing subjects \$25.

**H. Payment for a research-related injury:** None anticipated

### **IV. Data Collection and Protection**

#### **A. Data Management and Security:**

1. All data will be collected from the subjects and will be entered on a secure spreadsheet/ database. The study personnel will have access to this database.
2. All subject data will be de-identified and entered in a secure database.
3. Human subjects will be identified through coded information. No personal identifiers will be used.
4. Research coordinators
5. N/A
6. Data will be stored in a secure server.
7. None
8. None

**B. Sample / Specimen Collection:** No samples will be collected or stored as a part of the study.

**C. Tissue Banking Considerations:** None

**D. Procedures to protect subject confidentiality:** None

**E. Quality Assurance / Monitoring**

1. All data will be verified prior to entering in the database to ensure reliability.
2. No

## **V. Data Analysis and Reporting**

**A. Statistical and Data Analysis:** All data collected from the patients will be entered on a secured spreadsheet/ database. No patient identifiers will be used. Descriptive statistics will establish baseline characteristics and adverse event frequency. Data for the primary endpoint will be statistically analyzed via 2-tailed t-test. Data for the secondary outcome measures will be statistically analyzed for both within and between group changes via 2-tailed repeated measures ANOVA and or independent or dependent t-tests as appropriate. All ANOVAs will be followed by univariate post-hoc tests.

**B. Outcome:** The primary end point of the study is to compare differences in headache severity at 120 minutes between study medication and placebo. A statistically significant pain relief in the study medication arm when compared to the placebo arm will determine success of the study. The secondary end point will be to assess the safety and subject satisfaction with treatment.

**C. Study results to participants:** Once the study results are available, they will be conveyed to the subjects either in person during their regular office visit or via telephone calls

**D. Publication Plan:** We plan to publish the study upon completion and results available.

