### **C. Sample size, statistical methods, and power calculation**

1. A total of 26 subjects will be enrolled. Eligible subjects in the age group of 18-65 years will be enrolled at the University of Kansas Medical Center. Subjects will be randomized on 1:1 ratio. They will treat their first migraine episode with the first drug (study drug or placebo, depending upon which group they are randomized to) and then will cross over to the second drug.
2. This will be a double-blinded study. The drug bottles (study drug and placebo) will be given to the subjects in unlabeled bottles.
3. A maximum of 26 subjects will be enrolled in the study. All data collected from the subjects will be entered on a secured spreadsheet/ database. Descriptive statistics will establish baseline characteristics and adverse event frequency. Data for the primary endpoint will be statistically analyzed via 2-tailed t-test. Data for the secondary outcome measures will be statistically analyzed for both within and between group changes via 2-tailed repeated measures ANOVA and or independent or dependent t-tests as appropriate. All ANOVAs will be followed by univariate post-hoc tests.
4. Study results:  
Primary outcome change in visual analogue pain scale (VAS) 120 minutes after dose showed a similar decreases for placebo and drug with a slightly wider 95% CI for placebo. Planned secondary analysis based on satisfaction (satisfactory and very satisfactory compared to neutral and unsatisfied) was negative by Chi-square  
Post-hoc analysis was 50% or greater decrease in VAS compared to < 50% decreased was negative by chi-square

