  - Subjects, who in opinion of the Investigator, should not be enrolled in the study because of the precautions, warnings or contra-indications sections of the timolol Package Insert
3. Withdrawal/Termination criteria: Although we do not anticipate any adverse events, subjects who experience any adverse effect from the study drug will be withdrawn from the study. Since the study drug will be used only once there will be no need to taper the drug dose. There wont be any tests necessary upon withdrawal from the study. Also, subjects who do not have any migraines attacks in the given 8 weeks period will be dropped from the study.
4. The study subject will not participate in another research study while participating in this study.

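### The trial randomises treatment order across two attacks, but the primary t-test has no period or sequence term, at a cost in precision, power and possibly a shifted estimate

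*Combined protocol and SAP*

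**What the plan says.** Section II.C, item 1 sets the allocation: "Subjects will be randomized on 1:1 ratio". Subjects treat a first attack with one bottle "and then will cross over to the second drug". What is randomised is therefore the order of the two products.

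Section V.B defines the primary end point as the aim to "compare differences in headache severity at 120 minutes between study medication and placebo", and makes statistical significance the criterion of success. Section V.A gives the test: "Data for the primary endpoint will be statistically analyzed via 2-tailed t-test". The same sentence stands in II.B and II.C.3. None of these places says whether the test is paired, or mentions period, attack order or sequence. For secondary outcomes V.A lists "2-tailed repeated measures ANOVA and or independent or dependent t-tests as appropriate", again with no period factor.

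Two provisions can leave the orders with unequal numbers of complete pairs. Under II.D.3, "subjects who experience any adverse effect from the study drug will be withdrawn from the study". Under II.B, the closing visit takes place by 8 weeks even if a second attack has not been treated, and bottle 2 is released only after bottle 1 has been returned.

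Section II.C.4 already reports the primary result: similar falls in pain score on both products. It gives no within-subject contrast and mentions no adjustment for period.

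**The concern.** Settling that the t-test is paired would not settle this point. A paired test on timolol minus placebo still merges two groups whose expected differences are not the same if attack 1 and attack 2 differ for reasons other than the drug.

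Such a difference is plausible here. Instillation is taught at enrolment, and the protocol foresees missed drops, so technique may improve by the second attack. The first attack follows a neurology visit, whereas the second bottle may arrive by courier.

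At stake are the width of the interval, the power of the test that decides success and, with unequal orders, the treatment estimate itself. The trial already holds the information needed to remove the problem.

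**Working it through.** **The plan's own figure.** "A total of 26 subjects will be enrolled", justified in II.B by 90% power at the 5% level for 25% versus 65%. The pooled two-proportion formula, n = [z_a √(2 × 0.45 × 0.55) + 1.282 √(0.25 × 0.75 + 0.65 × 0.35)]² / 0.40², gives 31 per treatment two-sided (z_a = 1.960) and 25 one-sided (z_a = 1.645). A two-sided paired (McNemar) calculation gives 26 if the within-subject correlation is about 0.3. So 26 can be approached, but only for a binary outcome. It supplies no SD for a t-test on severity.

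**Inputs.** From the documents: two orders, two attacks, 26 subjects, 1:1, two-tailed t-test. Assumed, because the documents are silent:
- SD of the within-subject difference: 3 points.
- True effect: 0.66 × 3 = 1.98 points, chosen to give about 90% power with 26 pairs.
- Period difference π: 0, 1 or 2 points.
- Completers: 13:13 or 13:9.

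**Model.** Let d be timolol minus placebo within a subject, signed so that positive favours timolol. Let n1 be the timolol-first completers, n2 the placebo-first completers, and N = n1 + n2. Then d has mean τ + π in the first group and τ − π in the second.

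**Pooled paired test.**
- Shift in the estimate = π(n1 − n2)/N. At 13:13 it is 0. At 13:9 its size is 1 × 4/22 = 0.18 or 2 × 4/22 = 0.36 points.
- Expected variance = σ² + π² × 4 n1 n2 / [N(N − 1)]. At 13:13 the multiplier is 676/650 = 1.04, so 9 becomes 10.04 (π = 1) or 13.16 (π = 2).

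**Period-adjusted test.** The attack-1-minus-attack-2 difference has mean π + τ (timolol first) and π − τ (placebo first). Half the contrast between the groups is τ, free of π. Its standard error is (σ/2)√(1/n1 + 1/n2), with N − 2 degrees of freedom.

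**Break-even.** At 13:13 the pooled interval becomes the wider one when 1 + 1.04π² exceeds (2.0639/2.0595)² = 1.0042, with π in SD units. That is π of about 0.064 SD. At 13:9 it is about 0.20 SD, or 0.6 points at the assumed SD.

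**Results** (power and type I error by simulation, 200,000 runs per cell):

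| Completers | π (points) | Shift | Pooled interval vs adjusted | Power, pooled | Power, adjusted | Two-sided type I error, pooled |
|---|---|---|---|---|---|---|
| 13:13 | 0 | 0 | 0.2% narrower | 90% | 90% | 5% |
| 13:13 | 1 | 0 | 5% wider | 88% | 90% | 3.9% |
| 13:13 | 2 | 0 | 21% wider | 80% | 90% | 1.9% |
| 13:9 | 0 | 0 | 2% narrower | 84% | 83% | 5% |
| 13:9 | 1, against drug | 0.18 | 3% wider | 73% | 82-83% | 4.7% |
| 13:9 | 1, for drug | 0.18 | 3% wider | 87% | 82-83% | 4.7% |
| 13:9 | 2, against drug | 0.36 | 18% wider | 52% | 82-83% | 3.8% |
| 13:9 | 2, for drug | 0.36 | 18% wider | 87% | 82-83% | 3.8% |

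The 87% figures reflect bias towards the drug and are not a gain. At 16:10 the pooled two-sided type I error reaches at most about 5.8%.

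**The case against.** **The wording does not exclude period.** A two-sample t-test on period differences is itself a two-tailed t-test, so V.A permits the recommended analysis. This stands: the plan is silent on period. It remains true that nothing in V.A, II.B or II.C would lead an analyst to that test.

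**Not every period difference does harm.** Below about 0.064 SD at 13:13, or 0.20 SD at 13:9, the pooled interval is the narrower one. This stands and limits the point to non-trivial differences.

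**A reader might infer that false positives are inflated.** The figures do not support that. Overall two-sided error is below 5% at 13:13 and 13:9. The tails do become unequal: when the shift favours timolol, that tail rises from 2.5% to about 3.7% at 13:9, and to about 5.7% at 16:10 with a 2-point difference.

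**The sizes are assumed.** A 2-point period difference makes attack order matter as much as the drug. A 13:9 split needs all four losses in one order, and the protocol anticipates no adverse events and gives no rates. Both are fair, so the figures are a range and not a forecast. Imbalance can also arise by chance. No randomisation method beyond the ratio is stated; if it was simple, exactly 13:13 has probability 0.155 and 16:10 or worse 0.33.

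**Adjustment does not cure everything.** If what subjects expect of bottle 2 depends on which product came first, that is carry-over, which a period term does not remove. Withdrawal related to response can bias the adjusted estimate too. Both limits stand.

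**Conclusion.** The point holds as an improvement to the primary analysis. The design randomises order and the stated test does not use it. The main cost is precision and power, with a possible shift in the estimate of π(n1 − n2)/N in either direction when completers are unequal.

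With balanced orders the loss is small for a 1-point period difference (about two percentage points of power) and about ten points for a 2-point difference. With 13:9 completers, a period difference that opposes the drug costs roughly 10 to 30 points of power. All of this rests on the assumed SD, effect, period difference and split.

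A reader might infer that the result reported in II.C.4 is wrong, or would change on re-analysis. The documents do not support that: they give no counts by order, no period means and no within-subject contrast from which to judge it.

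**What to change.** In V.A, II.B and II.C.3, state the primary test as a two-tailed two-sample t-test comparing the attack-1-minus-attack-2 difference between the two randomised orders. Report half the contrast as the treatment effect, with its 95% CI. For complete pairs a mixed model with treatment, period and a random subject effect is equivalent.

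Because II.C.4 already gives results, keep the reported analysis and add the re-run beside it, clearly labelled as a period-adjusted re-analysis. Give the number of complete pairs in each order and the mean for each attack within each order, so that readers can see the period difference and any imbalance. State that the analysis assumes no carry-over and that withdrawal is unrelated to response.

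The cost is one sentence in three places, a re-run on data already held and one degree of freedom. If there is no period difference, the interval is 0.2% wider at 13:13 and about 2% wider at 13:9. The sample size is unchanged. The method of allocating order can no longer be changed in this trial.

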## **APPENDIX I: VULNERABLE POPULATIONS**

- I.** N/A
- II. Cognitively or decisionally impaired individuals:** Subjects with history of an underlying neurological or psychiatric condition which in the opinion of the investigator would contraindicate participation will be excluded from the study
- III. Children:**
- IV. Pregnant women:** Pregnant women will be excluded from the study
- V. Prisoners:** We do not foresee any prisoners to be enrolled in the study.
- VI. Students and/or Employees:**
  - A.** None
  - B.** None
  - C.** We will identify and enroll subjects in the age groups of 18-65 years.
